#### Notes:

- a Subjects are required to fast for at least 8 hours before the visit(s).
- b Visit 3 is a single visit occurring between Week 1 to Week 2.
- c For subjects that complete the Week 16 visit and will rollover to the nemolizumab LTE study, the Week 16 visit (Visit 7) will serve as the final study visit. See Section 7.6.1.
- A follow-up visit is required for subjects who discontinue after the Week 16 visit and will not rollover to the nemolizumab LTE study. The follow-up visit should occur 12 weeks after the last study drug injection. See Section 7.6.1.
- e Assessments to be conducted at the unscheduled visit(s) depend on the reason for the visit. See Section 7.6.2.
- Subjects who discontinue before the Week 16 visit should attend an early termination visit and a follow-up/final study visit 12 weeks after the last study drug injection. See Section 7.6.1.

CONFIDENTIAL Page 37 of 99

Galderma Research & Development, LLC Protocol Number: RD.06.SPR.116912 21-JUL-2020 Version 6.0

- g Patient-reported efficacy measurements (ACT and DLQI/cDLQI) should occur before investigator (efficacy and safety) assessments, blood sample collections, and study drug administration.
- h Peak and average pruritus NRS should be recorded by subjects once daily in the evening, beginning ≥ 2 weeks before Day 1.
- Sleep disturbance NRS should be recorded by subjects once daily in the morning, beginning ≥ 2 weeks before Day 1.
- Subjects will be asked to record the response (yes/no) to the following question each evening, "Did you apply the eczema medication your doctor gave you, to your skin today?", beginning ≥ 2 weeks before Day 1. See Section 7.5.8.1.1.
- Subjects with a history of asthma will complete the ACT at each study visit before physical examination and other investigator assessments. Subjects with de novo diagnosed asthma will complete the ACT beginning at the first visit of de novo diagnosis and at all follow-up study visits.
- Subjects aged 17 years or older will complete the DLQI, while subjects aged 12-16 years old will complete the cDLQI.

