#### 8.6.1.1 Adverse Events of Special Interest

An AESI is a noteworthy event for the study drug that should be monitored closely and reported immediately. See Section 8.6.1.4 for reporting procedure. An AESI can be either serious or non-serious.

Based on the potential risks of nemolizumab and the risks associated with biologics (and their biosimilar equivalents) in general (ie, class effects), the following AEs will be considered AESIs:

- Injection-related reactions
  - Anaphylactic reactions
  - Acute allergic reactions requiring treatment
  - Severe ISR (ie, lasting > 24 hours)
- Newly-diagnosed asthma or worsening of asthma
  - More specifically, subjects with a medical history of asthma must be referred to the physician who manages their asthma when:
    - ACT score ≤ 19; an ACT score ≤ 19 conveys asthma which may not be adequately controlled. An AESI is reported based on the investigator's clinical judgment of the managing physician's report.
    - PEF < 80% of the predicted value; an AESI should be reported.

    - Unexpected worsening of asthma is observed or reported. An AESI is reported based on the investigator's clinical judgment.
  - Subjects without a medical history of asthma must be referred to an appropriate respiratory physician/specialist when:
    - Signs and/or symptoms suggestive of asthma have been observed or reported. An AESI is reported based on the investigator's clinical judgment of the specialist's report.
    - Respiratory assessment suggests a decline in the subject's respiratory health. An AESI is reported based on the investigator's clinical judgment of the specialist's report.
- Infections
  - Any severe infection, or any infection requiring treatment with parenteral antibiotics, or oral antibiotics/antivirals/antifungals for > 2 weeks
- Peripheral edema: limbs, bilateral
- Facial edema

CONFIDENTIAL Page 63 of 99

Elevated ALT or AST (> 3 × ULN) in combination with elevated bilirubin (> 2 × ULN)

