3.4.2. Exclusion Criteria

Subjects will be excluded from the study if one or more of the following criterion are applicable:

- 1. Body weight < 30 kg.
- 2. Subjects meeting one or more of the following criteria at screening or baseline:
 - 2a. Had an asthma exacerbation requiring hospitalization in the preceding 12 months.
 - 2b. Reporting asthma that has been not well-controlled (ie, symptoms > 2 days per week, nighttime awakenings >1-3 times per week, or some interference with normal activities) during the preceding 3 months.
 - 2c. Asthma Control Test ≤ 19 (applies only for subjects with a history of asthma).

This document is confidential.

SAP Version: Final Version 3.0, 21-Sep-2020

Controlled Document ID: 3903A.01, Effective Date 29-Oct-2018

Filing requirements: TMF

- 2d. Peak expiratory flow < 80% of the predicted value.
- 3. Subjects with a current medical history of chronic obstructive pulmonary disease (COPD) and/or chronic bronchitis.
- 4. Cutaneous infection within 1 week before the screening visit or any infection requiring treatment with oral or parenteral antibiotics, antivirals, antiparasitics, or antifungals within 1 week before the screening visit. Subjects may be rescreened once the infection has resolved.
- 5. Requiring rescue therapy for AD during the run-in period, or expected to require rescue therapy within 2 weeks following the baseline visit.
- 6. Positive serology results for hepatitis B surface antigen [HBsAg] or hepatitis B core antibody [HBcAb], hepatitis C antibody, or human immunodeficiency virus [HIV] antibody at the screening visit:

Note: Subjects with a positive HBcAb and a negative HBsAg can be included in this clinical trial if hepatitis B surface antibody (HBsAb) is positive (considered immune after a natural infection).

- 7. Having received any of the treatments within the specified timeframe before the baseline visit as described in Protocol Section 8.3.3 (Table 3: Prior Treatments).
- 8. Subjects who failed to respond clinically to previous treatment with a biologic (eg, dupilumab) or a Janus kinase (JAK) inhibitor.
- 9. Pregnant women (positive serum pregnancy test result at the screening visit or positive urine pregnancy test at the baseline visit), breastfeeding women, or women planning a pregnancy during the clinical trial.

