10.7. Respiratory Assessment - Spirometry/Peak Expiratory Flow

At screening, the investigator should specifically question all subjects about any medical history of asthma and their respiratory health (eg, wheezing, allergies and infections). All subjects will have spirometry/Peak Expiratory Flow (PEF) performed at screening and baseline. For subjects reporting a medical history of asthma, PEF will be performed at each visit during the clinical trial. For subjects diagnosed with de novo asthma, PEF will be performed at all visits starting with the visit in which the diagnosis was confirmed.

Actual PEF (L/min), Predicted PEF Rate (L/min) and Actual PEF Rate of the predicted value (%) will be summarized descriptively by visit (scheduled visit only) as continuous variables. Absolute change from baseline will also be included in the descriptive analysis.

Also spaghetti plots over time will be displayed graphically for Actual PEF (L/min).

Number of subjects with abnormal PEF (actual PEF < 80% of the predictive value) will be summarized separately.

PEF assessment will be presented in listings.

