	14.3.1.2.1	Treatment Emergent Adverse Events (TEAEs) by System Organ Class and Preferred Term, All Causalities	Safety Population	Yes	Yes
	14.3.1.2.2	Treatment Emergent Adverse Events (TEAEs) by System Organ Class and Preferred Term, Study Drug Related	Safety Population	Yes	Yes
	14.3.1.2.3	Serious Treatment Emergent Adverse Events (TEAEs) by System Organ Class and Preferred Term, All Causalities	Safety Population	Yes	Yes

Header	Table Number	Name	Analysis Population	Interim Analysis	IDMC
	14.3.1.2.4	Serious Treatment Emergent Adverse Events (TEAEs) by System Organ Class and Preferred Term, Study Drug Related	Safety Population	Yes	Yes
	14.3.1.2.5	Treatment Emergent Adverse Events (TEAEs) by System Organ Class, Preferred Term, and Maximum Severity, All Causalities	Safety Population	Yes	
	14.3.1.2.6	Severe Treatment Emergent Adverse Events (TEAEs) by System Organ Class and Preferred Term, All Causalities	Safety Population	Yes	Yes
	14.3.1.2.7	Severe Treatment Emergent Adverse Events (TEAEs) by System Organ Class and Preferred Term, Study Drug Related	Safety Population	Yes	Yes
	14.3.1.2.8	Treatment Emergent Adverse Events (TEAEs) Leading to Permanent Discontinuation of Study Drug by System Organ Class and Preferred Term, All Causalities	Safety Population	Yes	Yes
	14.3.1.2.9	Treatment Emergent Adverse Events (TEAEs) Leading to Permanent Discontinuation of Study Drug by System Organ Class and Preferred Term, Study Drug Related	Safety Population	Yes	Yes
	14.3.1.2.10	Treatment Emergent Adverse Events (TEAEs) of Special Interest by System Organ Class and Preferred Term, All Causalities	Safety Population	Yes	Yes
	14.3.1.2.11	Treatment Emergent Adverse Events (TEAEs) Occurred in > 1 Subject by System Organ Class and Preferred Term, All Causalities	Safety Population	Yes	
4400	14.3.1.2.12	Treatment Emergent Adverse Events (TEAEs) Occurred in > 1 Subject by Preferred Term, All Causalities	Safety Population	Yes	
14.3.2		Listings of Deaths, Other Serious and Significant Adverse Events			
	14.3.2.1	Adverse Events leading to death	Safety Population	Yes	
	14.3.2.2	Listing of Serious Treatment Emergent Adverse Events (TEAEs)	Safety Population	Yes	
	14.3.2.3	Listing of Treatment Emergent Adverse Events (TEAEs) Leading to Permanent Discontinuation of Study Drug	Safety Population	Yes	
	14.3.2.4	Listing of Treatment Emergent Adverse Events (TEAEs) of Special Interest	Safety Population	Yes	

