	16.2.8.2.4	Physical Examination	Safety Population	Yes	
	16.2.8.2.5	Confirmed Pregnancy Test Results	Safety Population		Yes
	16.2.8.2.6	Respiratory Assessment – Peak Expiratory Flow (PEF)	Safety Population	Yes	
	16.2.8.2.7	Asthma Control Test (ACT)	Safety Population	Yes	
	16.2.8.2.8	Virology	Safety Population	Yes	
	16.2.8.2.9	Immunogenicity - Anti-drug Antibody (ADA) and Neutralizing Antibodies (NAb)	Safety Population	Yes	

Sponsor: Galderma Research & Development, LLC; Protocol No.: RD.06.SPR.116912, Version 6.0

Header	Table Number	Name	Analysis Population	Interim Analysis	IDMC
	16.2.8.2.10	Subjects with Childbearing Potential	Safety Population		
	16.2.8.2.11	Premenses Status	Safety Population		
	16.2.8.2.12	Subject with a drop by >= 15% from Baseline for either PEF or ACT	Safety Population		Yes
	16.2.8.2.13	Biomarker	Safety Population		
	16.2.8.2.14	All comments	Safety Population		

21. Potentially clinically significant ranges for laboratory tests

Test Parameter	Reference range (as per Lab Manual)		Potentially Clinically Significant Ranges (min and/or max limits)	SI Units			
	LLN	ULN					
SERUM							
White Blood Cell Count (WBC) 4.00		10.70	<2.5 at post-baseline, if baseline value ≥2.5 >13.0 at post-baseline, if baseline value ≤13	x10E9/L			
Neutrophils (absolute) 1.60		7.40	<1.5 at post-baseline, if baseline value ≥1.5 >9 at post-baseline, if baseline value ≤9	x10E9/L			
Eosinophils (absolute)	0.00	0.70	>0.8 at post-baseline, if baseline ≤0.8	x10E9/L			
Basophils (absolute)	0.00	0.20	>0.3 at post-baseline, if baseline value ≤0.3	x10E9/L			
Monocytes (absolute)	0.10	0.90	>1 at post-baseline, if baseline value ≤1	x10E9/L			
Lymphocytes (absolute)	1.00	4.00	<0.5 at post-baseline, if baseline value ≥0.5 >5.0 at post-baseline, if baseline value ≤5.0	x10E9/L			
Red Blood Cell Count		* 5.80	* <3.5 at post-baseline, if baseline value ≥3.5	x10E12/L			
*Male **Female	4.00	** 5.20	** >7.0 at post-baseline, if baseline value ≤7.0				
Hemoglobin	114.00	* 175.00	* <100 at post-baseline, if baseline value ≥100	g/L			
*Male **Female		** 160.00	** >190 at post-baseline, if baseline value ≤180				
Hematocrit			* 0.52	* <0.30 at post-baseline, if baseline value ≥0.30			
*Male **Female	0.36	** 0.46	** >0.6 at post-baseline, if baseline value ≤0.6	L/L			
мсу	78.00	98.00	98.00 <75 at post-baseline, if baseline value ≥75 >105 at post-baseline, if baseline value ≤105				

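### The only by-subject respiratory listing marked for the IDMC omits some subjects who cross the protocol's own PEF and ACT limits; the gap that remains is mainly for PEF

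*SAP*

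**What the plan says.** SAP Section 20 marks two listings for the IDMC: confirmed pregnancy tests (16.2.8.2.5) and Listing 16.2.8.2.12, "Subject with a drop by >= 15% from Baseline for either PEF or ACT". The 15% rule appears only in that index. No rationale is given, and the SAP does not say whether PEF there is in L/min or in % of predicted.

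The full PEF listing (16.2.8.2.6, "Respiratory Assessment – Peak Expiratory Flow (PEF)"), the full ACT listing (16.2.8.2.7) and, in SAP Section 18, Listing 14.3.2.4, "Listing of Treatment Emergent Adverse Events (TEAEs) of Special Interest", are marked for the interim analysis but not for the IDMC.

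Protocol 8.6.1.1 uses absolute limits for subjects with a history of asthma: "PEF < 80% of the predicted value; an AESI should be reported" and "ACT score ≤ 19; an ACT score ≤ 19 conveys asthma which may not be adequately controlled". The first calls for an AESI report; the second leads to referral, with an AESI at the investigator's judgment. SAP 10.7 and 10.8 summarise PEF and ACT at the same two limits.

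For subjects diagnosed during the study, the notes to Protocol 7.2 state: "Subjects with de novo diagnosed asthma will complete the ACT beginning at the first visit of de novo diagnosis". On the individual PEF display, SAP 10.7 states: "Also spaghetti plots over time will be displayed graphically for Actual PEF (L/min)".

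**The concern.** New or worsening asthma is a named AESI, and Protocol 5.3 has the IDMC monitor AESIs. In about 20 adolescents, with no earlier paediatric exposure to the drug, each respiratory case is reviewed as an individual. A committee member would expect the one respiratory listing supplied to name everyone who crossed a limit that the protocol itself treats as a signal.

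A fall measured relative to the subject's own starting value does not do that. The nearer a subject starts to the limit, the smaller the percentage fall needed to cross it, so the rule is least sensitive in the eligible subjects closest to the trigger. At stake is whether the IDMC can attach a name, a visit and a baseline to a crossing that it sees only as a count.

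**Working it through.** The plan gives no figure to reproduce here, so the check sets the listing rule against the protocol limits.

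**Inputs**
- Listing rule (SAP Section 20): with baseline b and later value v, a subject is listed if (b − v)/b ≥ 0.15, which is v ≤ 0.85 × b.
- Lowest eligible ACT is 20, because SAP 3.4.2 excludes "Asthma Control Test ≤ 19 (applies only for subjects with a history of asthma)". SAP 10.8 scores five items from 1 to 5, so the maximum is 25 and eligible baselines are 20 to 25.
- Lowest eligible PEF is 80% of predicted (SAP 3.4.2, criterion 2d).
- Baseline is the last measurement before the first dose (SAP 6.2).

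**ACT, every eligible baseline**

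| Baseline | 0.85 × baseline | Highest score listed | Fall to 19 | Scores ≤19 not listed | Scores ≥20 listed |
|---|---|---|---|---|---|
| 20 | 17.00 | 17 | 5.0% | 19, 18 | none |
| 21 | 17.85 | 17 | 9.5% | 19, 18 | none |
| 22 | 18.70 | 18 | 13.6% | 19 | none |
| 23 | 19.55 | 19 | 17.4% | none | none |
| 24 | 20.40 | 20 | 20.8% | none | 20 |
| 25 | 21.25 | 21 | 24.0% | none | 20, 21 |

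Five crossings are unlisted: 20→19, 20→18 (10.0%), 21→19, 21→18 (14.3%) and 22→19. From a baseline of 23 or more, every crossing is listed.

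**PEF, as % of predicted, holding the predicted value constant (an assumption)**

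A crossing is unlisted when 0.85 × b < v < 80. Such values exist only if b < 80/0.85 = 94.1.

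| Baseline, % predicted | Listed at or below | Crossings not listed |
|---|---|---|
| 80 | 68.0 | above 68.0, below 80 |
| 85 | 72.25 | above 72.25, below 80 |
| 90 | 76.5 | above 76.5, below 80 |
| 94.1 | 80.0 | none |
| 100 | 85.0 | none |

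If 15% were read as percentage points of predicted, the band of affected baselines would be 80% up to 95%.

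**De novo asthma.** ACT starts at the diagnosis visit, so a subject diagnosed after the first dose has no baseline ACT and the percentage fall is undefined. PEF is measured in every subject at screening and baseline (Protocol 8.6.9.3), so selection on PEF remains possible.

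**What else reaches the IDMC (SAP Sections 18 and 19)**
- Tables 14.3.4.4.4 (abnormal PEF) and 14.3.4.4.6 (ACT ≤19) count subjects at the protocol limits but do not identify them. Under SAP 6.1, repeat and unscheduled values stay out of summary tables unless stated otherwise.
- Table 14.3.4.4.3 summarises PEF by visit, scheduled visits only (SAP 10.7).
- Table 14.3.1.2.10 gives AESIs by system organ class and preferred term, not by subject.
- Table 14.3.4.4.7 summarises clinically significant respiratory examination findings.
- Figure 14.3.4.4.9 plots ACT for each subject. ACT is an absolute score, so a value of 19 or less can be read directly, including in de novo subjects.
- Figure 14.3.4.4.8 plots PEF for each subject in L/min. The 80% limit then lies at a different height for each subject and cannot be read off.

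**The case against.** The strongest reply is that the listing complements the fixed limits and does not replace them. No document says it should reproduce the referral or AESI triggers. A relative-fall screen exists to pick up subjects who decline while still above a limit, so listing 25→21 is the screen doing its job. A reader might take such entries as errors; they are not.

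A reader might also infer that the IDMC cannot see the unlisted crossings. The documents do not support that. The committee gets counts at both limits, the AESI table and both individual plots. The ACT plot largely covers the ACT omissions and the de novo cases. Nor is a de novo subject shut out of the listing, since PEF can still select that subject. In subjects with a history of asthma, PEF below 80% should be reported as an AESI, and Protocol 8.6.1.4 requires AESIs to be recorded within 24 hours.

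Finally, SAP Section 13 lets the IDMC ask for other outputs, and the IDMC charter, which is not among the documents, may specify more.

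All of this stands and limits the point. It does not close the PEF gap: a fall below 80% from a baseline of 80% to about 94% may be counted, yet not be attributable to a subject from the outputs indexed for the IDMC. The right to request more helps only once a member has noticed the omission.

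**Conclusion.** The point holds as a gap in by-subject identification, mainly for PEF. Listing 16.2.8.2.12 omits crossings of 80% of predicted from baselines of 80% to about 94.1%, and five ACT crossings from baselines of 20 to 22. It cannot select a de novo subject on ACT. For ACT the individual plot largely makes this good; for PEF no output indexed for the IDMC does.

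The ACT result is exact enumeration. The PEF result assumes a constant predicted value. No share of subjects is offered, because the documents give neither the distribution of baseline PEF nor its variability over time. The number affected will be small: post-baseline PEF and ACT are scheduled only for subjects with a history of asthma or de novo asthma, within about 20 enrolled. This is a worthwhile improvement to safety monitoring, not a failure of it.

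**What to change.** 1. Keep the 15% criterion in Listing 16.2.8.2.12 and add: or any post-baseline PEF below 80% of predicted, or any post-baseline ACT of 19 or less, whether or not a baseline exists. State the PEF unit used for the 15% rule. This adds the five missed ACT cases, every PEF crossing now omitted, and any de novo subject with ACT of 19 or less. Alternatively, mark Listings 16.2.8.2.6 and 16.2.8.2.7, already planned for the interim analysis, for the IDMC.
2. Draw Figure 14.3.4.4.8 in % of predicted with a line at 80%, and amend SAP 10.7 to match. That section already has the variable among its summaries.

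Unscheduled values need no new rule for the listing, since SAP 6.1 already includes them in listings. The cost is one selection condition (or two index marks), one axis change and a slightly longer listing. The limits are the protocol's own, so no clinical threshold changes.

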- In addition, summary of hematology, chemistry and urinalysis using potentially clinical significant ranges will be provided by visit. Potentially clinically significant laboratory ranges are presented in section 21 (Potentially clinically significant ranges for laboratory tests).

Distribution of Aspartate Aminotransferase (AST), Alanine Aminotransferase (ALT), Alkaline Phosphatase (ALP), Total bilirubin and Creatinine Phospokinease (CPK) will be displayed graphically with maximum post-baseline values. Also spaghetti plots over time will be displayed graphically for those five parameters.

By-subject listing for subjects with at least one abnormal results (out of reference range) will be provided for hematology and clinical chemistry.

By-subject listing for subjects with at least one potentially clinically significant results will be provided for hematology, clinical chemistry and urinalysis.

All laboratory data will be listed.

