10.4. Vital Signs, Height and Weight

Vital signs will include pulse rate, systolic and diastolic blood pressure (after the subject has been sitting for at least 5 minutes), and body temperature.

Vital Signs are performed at Screening, Baseline, Week 1- 2, Week 4, Week 8, Week 12, Week 16, Week 24 follow-up, Unscheduled Visits and Early Termination Visit.

Height will be measured at screening and designated visits; weight will be measured at all visits.

Vital signs, height and weight will be summarized descriptively by visit (scheduled visits only) as continuous variables. Absolute changes from baseline will be included in the summary tables. For vital signs parameters, last post-baseline results during treatment period will be summarized in the table.

Shift from baseline in vital signs using normal, abnormal cs, abnormal ncs results will be provided at post-baseline visits (scheduled visits only) and last post-baseline results during treatment period will be included in the shift table.

In addition, vital signs and weight will be summarized using potentially clinically significant ranges.

By-subject listing for subjects with at least one potentially clinically significant results will be provided for vital signs.

All vital signs, height and weight data will be listed.

Potentially Clinically Significant Ranges for Vital Signs and Weight:

Parameter	SI Units	Potentially Clinically Significant Ranges
Pulse rate	beats/min	< 50 (low) and a decrease > 20 from Baseline or >110 (high) and an increase > 20 from Baseline
Temperature	°C	< 35 (low) or > 38 (high)
Diastolic blood pressure	mmHg	< 50 (low) and a decrease > 10 from Baseline or >90 (high) and an increase > 10 from Baseline
Systolic blood pressure	mmHg	< 90 (low) and a decrease > 20 from Baseline or >135 (high) and an increase >20 from Baseline
Weight	kg	<95% or >105% of change from baseline

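### As written, the potentially clinically significant (PCS) rules for red cell count, haemoglobin, haematocrit (SAP 21) and weight (SAP 10.4) are mis-specified and would give wrong counts if programmed literally

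*SAP*

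**What the plan says.** SAP 10.3 states that a "summary of hematology, chemistry and urinalysis using potentially clinical significant ranges will be provided by visit" and points to Section 21 for the limits. It also promises a by-subject listing of PCS results. SAP 10.4 does the same for vital signs and weight, with its own small table of ranges.

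In Section 21 the rows for red cell count, haemoglobin and haematocrit name the sexes in the first column, one asterisk for male and two for female. The upper limit of normal is then given separately for each sex with those marks (haemoglobin: 175 g/L male, 160 g/L female). The PCS column of the same rows reads:

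- Red cell count: "<3.5 at post-baseline, if baseline value ≥3.5" with the male mark; ">7.0 at post-baseline, if baseline value ≤7.0" with the female mark.
- Haemoglobin: "<100 at post-baseline, if baseline value ≥100" with the male mark; ">190 at post-baseline, if baseline value ≤180" with the female mark.
- Haematocrit: "<0.30 at post-baseline, if baseline value ≥0.30" with the male mark; ">0.6 at post-baseline, if baseline value ≤0.6" with the female mark.

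For weight, SAP 10.4 gives the range as "<95% or >105% of change from baseline".

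The table and listing index (SAP 18) marks the PCS haematology summary (14.3.4.1.1.3) and the PCS vital signs and weight summary (14.3.4.2.3) for the IDMC. It marks the PCS haematology listing (14.3.4.1.1.5) for the interim analysis.

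**The concern.** A PCS table is meant to pick out the few values that deserve a second look. That works only if each rule applies to the subjects it is meant for and leaves unremarkable values alone. Here three haematology rows appear to tie direction to sex, one rule has a limit and a baseline condition that do not match, and the weight rule applies limits centred on 100% to a change, which is centred on 0%.

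The SAP gives no reason for flagging only falls in boys and only rises in girls. Programmers who follow the text produce wrong counts. Programmers who guess the intent depart from a final SAP without a record of it. Protocol 9.4.3.5 also calls for the number and percentage of subjects with abnormal vital signs and weight of clinical concern, and the SAP 10.4 weight line is the stated range for weight.

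**Working it through.** No sample-size, power or alpha figure is involved, and the plan states no figure to reproduce. The check sets the rows side by side and applies each rule to example values. The example values are illustrations, not trial data.

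**Step 1: is the sex marking deliberate or a misprint?** Other two-sided rows in Section 21 (white cells, lymphocytes, MCV, platelets, sodium) print a low and a high limit with no sex mark, so both apply to everyone. Where CPK, GGT and uric acid are split by sex, a limit is printed for each sex. Only the red cell, haemoglobin and haematocrit rows give one direction to each sex. The pattern repeats across three rows and six limits, so it is unlikely to come from the PDF conversion.

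**Step 2: count the rules.** 3 tests × 2 directions × 2 sexes = 12 possible flags. As marked, the flags that exist are low in males (3) and high in females (3), so 6 exist and 6 do not. The sex split is not given. With f females among about 20 subjects, f have no low flag and 20 − f have no high flag. Whatever f is, every subject lacks one direction on all three tests. If half are female (an assumption), 10 have no low flag.

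**Step 3: apply the haemoglobin rules (g/L).** As written, flag if (male, value < 100, baseline ≥ 100) or (female, value > 190, baseline ≤ 180).

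| Baseline to post-baseline | Male, as written | Female, as written | Both limits for both sexes, one number (190 used for illustration) |
|---|---|---|---|
| 130 to 95 | flagged | not flagged | flagged |
| 130 to 85 | flagged | not flagged | flagged |
| 170 to 195 | not flagged | flagged | flagged |
| 185 to 195 | not flagged | not flagged | flagged |
| 130 to 130 | not flagged | not flagged | not flagged |

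**Step 4: the 190/180 pair.** The last-but-one pattern, 185 to 195, shows the gap: a baseline above 180 and up to 190 that later passes 190 is never flagged. Such a baseline already exceeds both printed upper limits of normal (175 and 160), so very few subjects could be affected. The other fixed-value rules in Section 21 use the same number for the limit and the baseline condition.

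**Step 5: the weight rule.** Let b be baseline weight, w post-baseline weight and c = 100 × (w − b)/b. Literally, flag if c < 95 or c > 105. For 50 kg rising to 51 kg, c = 100 × 1/50 = 2, and 2 < 95, so the subject is flagged. For no change, c = 0, also flagged. Changes of −10, −6, −3, 0, +2, +4, +6, +10 and +20% at baselines of 30, 40, 50, 61 and 70 kg were all flagged. Only a gain of 95% to 105% escapes, for example 30 kg rising to between 30 × 1.95 = 58.5 kg and 30 × 2.05 = 61.5 kg.

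Read as w < 0.95b or w > 1.05b, the changes of −3, 0, +2 and +4% are not flagged and the other five are. The band is then 0.05 × 30 = 1.5 kg at 30 kg, 0.05 × 61 = 3.05 kg at 61 kg and 0.05 × 70 = 3.5 kg at 70 kg.

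**The case against.** The strongest reply is that little safety information is at risk, and most of that reply stands.

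- **The values remain visible.** A reader might infer that a girl whose haemoglobin fell to 80 g/L would be hidden from the IDMC. The documents do not support that. The haematology summary (14.3.4.1.1.1, IDMC and interim) includes minimum post-baseline values, so 80 would be printed there, though not tied to a subject or sex. The reference-range shift table (14.3.4.1.1.2, IDMC and interim) would count a shift to low, since the lower limit of normal is 114. The interim listing of abnormal results (14.3.4.1.1.4) would name her. Protocol 8.6.2 has the investigator judge each out-of-range result and report clinically significant new or worsened ones as adverse events. Weight and its absolute change reach the IDMC in Table 14.3.4.2.1.
- **The weight line has an obvious intended meaning.** Limits placed evenly around 100% make sense only as a percentage of baseline weight. A table flagging nearly everyone should also be caught by the output review in SAP 17.
- **The PCS results are descriptive.** The documents shown tie no test or stopping rule to them.

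What the reply does not meet is that the sex marks are unambiguous by the table's own key, give plausible-looking output, and would not stand out on review as the weight flag would. A second programmer checking against the same SAP would reproduce the same rule.

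**Conclusion.** The specification is wrong as written for four parameters: red cell count, haemoglobin, haematocrit and weight. If programmed literally, it gives wrong counts in IDMC Tables 14.3.4.1.1.3 and 14.3.4.2.3 and wrong entries in interim listing 14.3.4.1.1.5. In size, 6 of 12 sex-by-direction haematology flags are missing, and the weight flag is met by effectively every subject. The 190/180 mismatch is a minor inconsistency with very small reach.

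A reader might go further and conclude that the safety flags sent to the IDMC are wrong in general. The documents do not show that. They contain a specification and no programmed output, and the fault is shown for four parameters only. The loss is the correct PCS count and listing entry. It does not touch the primary PK results or the reference-range outputs. The conclusion assumes that the asterisks in the PCS column follow the key in the same row and that the weight change is taken as a percentage of baseline.

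**What to change.** - **SAP 21, red cell count, haemoglobin, haematocrit:** remove the sex marks from the PCS limits so that low and high limits apply to both sexes, as in the other two-sided rows. Alternatively, print a low and a high limit for each sex.
- **SAP 21, haemoglobin high rule:** the sponsor should reconcile 190 with 180 so that the limit and its baseline condition use the same number. Nothing in the documents shows which of the two is the misprint.
- **SAP 10.4, weight:** restate the rule as post-baseline weight below 95% or above 105% of baseline weight.

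The cost is a few words in two SAP tables and the matching flag code. No new data are needed. A few more haematology values may be flagged and far fewer weights than under the literal rule. If the programs already follow the intended reading, the correction simply brings the SAP into line with them.
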